- Vital signs, methemoglobin and oxygen saturations
- Oxygen flow requirements
- Respiratory Failure Status
- Clinical status using an 8-point NIAID ordinal scale ([Table 1](#))
- Upon discontinuation of INOpulse, irrespective of reason, subjects should be monitored for 1 hour for symptoms of pulmonary rebound which include hypoxemia, bradycardia, tachycardia, systemic hypotension, shortness of breath, near-syncope, and syncope. SpO2, BP and vital signs should be measured every 30 minutes for 1 hour.
- Adverse event(s) assessment
- Download usage data from the INOpulse device

If a subject has completed **End of Treatment** (off INOpulse) and is **still hospitalized** (not discharged), daily assessments (up to Day 28 or day of discharge if earlier) will be performed as follows:

- Respiratory Failure status
- Clinical status using an 8-point NIAID ordinal scale ([Table 1](#))
- Adverse event(s) assessment
- Concomitant medications

At time of hospital **discharge**, if before the End of Study assessment, the following assessments will be completed:

- CT scan or chest x-ray prior to discharge, as clinically indicated
- Duration of hospitalization
- Respiratory Failure Status
- Clinical status using an 8-point NIAID ordinal scale ([Table 1](#))
- Adverse event(s) assessment
- Concomitant medications

If a subject has been discharged from the hospital, the following assessments will be completed on **Day 7, Day 14 and Day 28** via telephone:

- Respiratory Failure status
- Clinical status using an 8-point NIAID ordinal scale ([Table 1](#))
- Adverse event(s) assessment
- Concomitant medications

End of Study: Thirty (30) days following the last dose of INOpulse, subjects will be assessed for the following via telephone (or in person in the unlikely event the subject is still hospitalized):

- Respiratory Failure status
- Clinical status using an 8-point NIAID ordinal scale ([Table 1](#))
- Adverse event(s) assessment
- Concomitant medications

At **Early Discontinuation** (if applicable), the following assessments will be completed:

- CT scan or chest x-ray any time prior to discharge, as clinically indicated

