9. SUBJECT DISCONTINUATION, WITHDRAWAL AND TERMINATION FROM THE STUDY

9.1. Subject Discontinuation from Study Drug/Device

Vital status (whether alive or dead) will be determined on all subjects who prematurely discontinue. The specific reason for discontinuation will be documented. Subjects may be discontinued due to the following:

1. In the opinion of the Investigator, it is in the subject's best interests to discontinue study drug.
2. Subject no longer wishes to continue using the drug/device.
3. A subject becomes pregnant.
4. In the opinion of the Investigator, the subject experiences clinically significant rebound defined as clinically significant cardiopulmonary instability such as systemic arterial oxygen desaturation, hypoxemia, bradycardia, tachycardia, systemic hypotension, shortness of breath, near-syncope, and syncope occurring after acute withdrawal of study drug.
5. If methemoglobin $> 7\%$ is sustained or severe respiratory failure, multi-organ failure and/or other conditions arise that impair the ability of the subject to receive INOpulse, INOpulse therapy should be permanently discontinued.

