10.1.14. Symptomatic Rebound Testing Post INOpulse Discontinuation

Subjects receiving INOpulse should be monitored every 30 minutes for 1 hour after discontinuation of treatment, including early discontinuation subjects, for signs and symptoms of rebound (eg, systemic arterial oxygen desaturation, hypoxemia, bradycardia, tachycardia, systemic hypotension, shortness of breath, near-syncope, and syncope). If symptomatic rebound is observed, treatment with INOpulse should be re-started and the Investigator should contact Bellerophon.

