8.0 Study Design

This is a randomized, double-blind, placebo-controlled study to assess the efficacy and safety of pulsed iNO compared to placebo in subjects with COVID-19 who are hospitalized and require supplemental oxygen without assisted ventilation. Subjects will receive placebo or iNO125 mcg/kg IBW/hr for 24 hours daily until resolution of hypoxemia, protocol defined respiratory failure, hospital discharge or Day 28, whichever occurs first. Subjects will be followed through 30 days after discontinuation of INOpulse therapy to assess their clinical status.

An unblinded independent Data Monitoring Committee (DMC) will review safety data including adverse events and adverse events of special interest. The roles and responsibilities of the DMC, including membership, scope, frequency of meetings and communication plan are defined in the current DMC charter on file with the sponsor. DMC members will evaluate the overall safety profile of INOpulse for subjects who received treatment compared to subjects who received the placebo.

There is one planned interim analyses for this study in order to assess potential futility of the INOpulse group versus placebo based on the primary endpoint of death/respiratory failure (DRF). The interim analysis will occur after the first 100 subjects complete 28 days on the protocol, and will evaluate interim safety and potential futility. The DMC will make the determination to either continue the trial, or to stop the trial due to safety concerns or futility, based on DRF. The interim analyses results will be evaluated by the DMC based on pre-specified criteria and stopping rules as detailed in this SAP. The final analysis will be conducted using the full sample size of all subjects enrolled, according to the population definitions ("Analysis Sets") described in Section 11.0 below.

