A summary of adverse events leading to discontinuation of INOpulse will be provided, grouped by body system and preferred term.

The following events will be considered AEs of special interest (AESI). In addition, AESIs will also include medical device deficiencies and/or complaints.

- All respiratory AEs
- Incidence of methemoglobin (MetHb) levels $\geq 7.0\%$ in blood

- New symptoms that may be associated with local nasal irritation: nasal erythema, epistaxis and/or coryza
- New or worsening symptoms of left heart failure or pulmonary edema
- Any decrease in systemic oxygenation measured by either PaO₂ or oxygen saturation by pulse oximeter (SpO₂) deemed by the Investigator to be clinically significant
- New symptoms that may be due to rebound effects associated with a temporal acute withdrawal of study drug (i.e., symptoms occurring within 20 minutes of acute withdrawal and including those associated with device malfunction or failure): hypoxemia, bradycardia, tachycardia, systemic hypotension, syncope, near-syncope, ventricular fibrillation and/or cardiac arrest.

All adverse events (including non-treatment-emergent events) recorded on the CRF will be listed.

Handling of missing or partial AE start dates is defined in Appendix 2.

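### The SAP's 20-minute window for rebound AESIs closes before the protocol's first scheduled check at 30 minutes, so rebound may be under-counted or impossible to classify

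*SAP*

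**What the plan says.** The AESI list in SAP 13.6.2 includes symptoms attributed to rebound and limits them, with an i.e., to "symptoms occurring within 20 minutes of acute withdrawal". The bullet also takes in withdrawals caused by device malfunction or failure. Neither document explains the choice of 20 minutes.

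The protocol monitors for longer. Its synopsis, under End of Treatment, says that "subjects should be monitored for 1 hour for symptoms of pulmonary rebound" and that "SpO2, BP and vital signs should be measured every 30 minutes for 1 hour". The synopsis repeats both under Early Discontinuation, and footnote 8 to Table 2 repeats the measurement interval. Section 10.1.14 says that subjects "should be monitored every 30 minutes for 1 hour after discontinuation of treatment". Section 9.1 describes clinically significant rebound as cardiopulmonary instability "occurring after acute withdrawal of study drug" and sets no time limit.

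On use and reporting, SAP 8.0 has the unblinded DMC "review safety data including adverse events and adverse events of special interest". Appendix 4 contains no AESI table or listing. SAP 13.6.2 defines treatment emergence by onset date, and SAP Appendix 2 imputes dates only.

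**The concern.** Rebound after withdrawal is a risk that the protocol monitors for by name. Its hour of observation after stopping, applied to both blinded arms, is the natural source for comparing rebound between them. The SAP then defines the countable event by a window that ends before the first scheduled measurement.

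Two things are at stake. Events that arise later in the monitored hour are not labelled as rebound. For events found by measurement rather than by complaint, the SAP does not say how anyone would decide whether onset came before or after 20 minutes. A rebound AESI count made under this rule could look lower than what the monitoring found. With no AESI table planned, the comparison by arm may not be shown at all.

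**Working it through.** No sample-size or power formula applies. The check sets the window against the schedule and then reads the other AESI bullets for overlap.

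**Inputs.** Window: 20 minutes (SAP 13.6.2). Monitored period: 60 minutes, with measurements every 30 minutes (protocol synopsis and 10.1.14). This puts the scheduled post-withdrawal checks at 30 and 60 minutes.

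**Schedule against window.** The first check comes 30 − 20 = 10 minutes after the window closes, and the second 60 − 20 = 40 minutes after. So 0 of 2 checks lie inside. For illustration only, a 30-minute window would contain 1 of 2 checks and a 60-minute window 2 of 2. The window covers 20/60 = 33% of the monitored time and leaves 40/60 = 67% outside. These are shares of time, not of events.

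**What happens to an event that starts at 21 to 60 minutes:**

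| Event | Rebound AESI | AESI under another bullet | In AE tables and listings if recorded |
|---|---|---|---|
| Tachycardia, bradycardia, hypotension, near-syncope, syncope | No | Not named in any | Yes |
| Desaturation judged clinically significant | No | Yes, oxygenation bullet, no time limit | Yes |
| Shortness of breath recorded as a respiratory AE | No (not in the SAP's rebound list at any time) | Yes, respiratory AE bullet, no time limit | Yes |

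**Onset.** The SAP rule depends on when a symptom occurs. A symptom that starts at 15 minutes and is noted at 30 qualifies if the 15 minutes is recorded. A heart rate or blood pressure first found abnormal at 30 minutes began at some unknown point between 0 and 30, on either side of the cut-off. The SAP gives no clock-time rule to resolve this. Whether the case report form collects AE clock times cannot be seen from the two documents.

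**Symptom lists.** Shortness of breath is among the protocol's rebound symptoms but not in the SAP's rebound bullet. Ventricular fibrillation and cardiac arrest are in the SAP's bullet but not in the protocol's list.

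**The case against.** The strongest reply is that a monitoring period may properly be longer than an attribution window, so the two times do not contradict each other by themselves. A short window makes the label more specific. The SAP bullet also covers withdrawal through device failure, where the checks scheduled after discontinuation may not apply. This stands as far as it goes. The documents do not settle which window is the right case definition of rebound, and this point does not claim that they do.

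A reader might infer four stronger things, and the documents support none of them:

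- That anything first found at a scheduled check is excluded. The SAP tests occurrence, not detection, so such an event is undetermined rather than certainly out.
- That only unscheduled reports can qualify. On the synopsis wording, symptoms are watched throughout the hour, and the 30-minute interval belongs to SpO2, blood pressure and vital signs. Section 10.1.14 is worded more loosely.
- That these events are hidden from the DMC. SAP 13.6.1 gives the DMC unblinded AE tables by arm and patient listings, and SAP 8.0 has it review AEs as well as AESIs. Its charter is not among the documents.
- That 33% or 0% of rebound events would be counted. The first figure needs uniform onset over the hour. The second needs every event to be dated to the check that found it. The documents state neither.

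The objection does not reach the haemodynamic and syncopal events at 21 to 60 minutes. No other AESI bullet names them, and a table by system organ class and preferred term does not separate a tachycardia after withdrawal from one during treatment.

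**Conclusion.** The mismatch is real and worth correcting as an inexpensive improvement. The SAP window is not aligned with the protocol's hour of monitoring or with its untimed description of rebound. No scheduled check falls within the window, and two thirds of the monitored time falls outside it. Tachycardia, bradycardia, hypotension, near-syncope or syncope beginning at 21 to 60 minutes loses the rebound AESI label, and measured abnormalities first seen at 30 minutes may not be classifiable.

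The loss is confined to rebound classification. AE capture, the efficacy endpoints and the named safety endpoint (AEs leading to study drug discontinuation) are unaffected. The conclusion assumes that the checks fall at 30 and 60 minutes after stopping, and that no rule for AE clock time exists outside the two documents. The number of events affected is unknown.

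**What to change.** Reconcile the SAP's rebound window and symptom list with protocol Sections 9.1 and 10.1.14 and the synopsis, and give the reason for 20 minutes if it is kept. Which clinical definition of rebound applies is for the sponsor to settle.

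For the analysis:

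- Tabulate rebound events by arm on the Full Safety Set over the full monitored hour, with onset within 20 minutes as a sub-category.
- State how onset is assigned when an event is first found at a scheduled check. One workable rule is to count it in the hour total and show it on a separate line as onset not determined, unless a start time was recorded.
- State how withdrawals through device malfunction or failure are handled where the scheduled checks were not done.
- Add an AESI table by arm to Appendix 4.

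The cost is some SAP wording, one table and confirmation that AE onset times are available. The monitoring schedule and clinical management do not change. The downside is a higher and less specific rebound count in both arms, which the 20-minute sub-category offsets in part.

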13.6.3 Deaths and Serious Adverse Events

The number and percentage of subjects reporting a SAE, by SOC and PT will be summarized by treatment group.

All deaths and SAEs will be presented in a by-subject level listing.

13.6.4 Laboratory Data

All laboratory parameters collected, along with change from baseline, will be summarized (n, mean, std, median, Q1, Q3, min, max) by treatment group and study time point. The lab parameters will include:

- Hematology - CBC
- Chemistry
 - Sodium
 - Potassium
 - Chloride
 - CO₂
 - BUN
 - Creatinine
 - Glucose
- Liver Function Tests (LFTs)
 - AST
 - ALT
 - Total Bilirubin
- Lipid/Protein Panel
 - Triglycerides
 - High Sensitivity Cardiac Troponin (HS-cTN)
 - Procalcitonin
 - Ferritin
 - Fibrinogen
 - D-dimer
 - NT-proBNP

- LDH
- Factors/Other Proteins
 - CRP
 - Von Willebrand's Factor
 - Factor VIII Activity
 - Protein C
 - Protein S
 - Homocysteine
 - Antithrombin 3
 - Thrombelastography (TEG)
 - G6PD deficiency
 - Prothrombin gene G2021A

Laboratory parameters will be grouped this way in the summary tables. Abnormal values for selected parameters will be graded by the central laboratory using criteria based on CTCAE Version 5.0 (SAP Appendix 3).

13.6.5 Vital Signs

Values for heart rate (HR), respiratory rate (RR), blood pressure (BP, systolic and diastolic), and temperature, and oxygen flow rate will be summarized (n, mean, std, median, Q1, Q3, minimum, and maximum) by treatment group and study time-point along with the change from baseline for each parameter at each scheduled post-baseline assessment.

All vital sign values for all subjects will also be provided in by-subject listings.

13.6.6 Other Observations Related to Safety

By-subject listings for physical examination, methemoglobin and 12-lead ECG findings will be provided.

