10.1.12. Methemoglobin

Methemoglobin will be assessed prior to initiating INOpulse, during the 1st hour (every ½ hour) of the first dose of INOpulse and approximately 4-5 hours after initiating INOpulse therapy. Methemoglobin should be < 3% and SpO₂ >89% (with supplemental O₂ required) prior to continuing with treatment.

Following initiation of treatment, methemoglobin will be assessed twice daily while on INOpulse. Levels should not exceed >7%, otherwise the study drug should be interrupted and/or discontinued.

Sponsor will provide Masimo RAD-57 with rainbow probe to monitor methemoglobin in subjects treated with INOpulse.

Criteria for Study Drug Interruption: If methemoglobin exceeds 7%, SpO₂ falls below 80%, or clinically significant iNO-related adverse events are observed, INOpulse therapy should be interrupted. INOpulse therapy may be re-started at the discretion of the Investigator.

Criteria for Study Drug Discontinuation: If methemoglobin > 7% is sustained or severe respiratory failure, multi-organ failure and/or other conditions arise that impair the ability of the subject to receive INOpulse, INOpulse therapy should be permanently discontinued. Severe respiratory failure does not include subjects that require use of High Flow Nasal Cannula \leq 15L/minute (these subjects can continue to receive INOpulse treatment).

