10.1.16. Drug Dispensing – Treatment Period

Prior to drug administration, the INOpulse® delivery device will be programmed and set up as per the INOpulse® Instructions for Use. Subjects will be instructed to notify the clinic staff if they hear an audible alert tone and/or if they notice flashing/steady amber or red lights from the INOpulse® delivery device during drug administration. Subjects will use the INOpulse for 24 hours daily until resolution of hypoxemia, protocol defined respiratory failure, hospital discharge or Day 28, whichever occurs first. In instances where continuous INOpulse dosing is not feasible (eg, due to PPE limitations), INOpulse should be used a minimum of 12 hours daily. Subjects may use 1 to 4 cartridges daily depending upon the duration of treatment (maximum of 28 days).

Safety will be assessed throughout the study by monitoring vital signs, methemoglobin, SpO₂ and adverse events.

All devices and cartridges will be returned to the Sponsor at the end of the study.

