13.6.2 Adverse Events

Treatment-Emergent Adverse Events (TEAEs) are defined as any AEs with an onset date on or after the date of the first dose of IP or any worsening of a preexisting medical condition/AE with onset after the start of IP and throughout the study. An AE leading to treatment discontinuation is defined as an AE where action taken on study drug is Drug Withdrawn. AEs will be coded using the Medical Dictionary for Regulatory Activities MedDRA version 23.0.

An overall summary of TEAEs, including the number of events reported, the number and percentage of participants reporting at least one TEAE, the number and percentage of participants discontinuing due to an adverse event, the number and percentage of participants with at least one serious adverse event, and the number and percentage of deaths will be presented.

The most frequent adverse events ($\geq 5\%$) will be compared between the INOpulse and placebo groups using a forest plot. The forest plot will display odds ratios of the incidence rate for each AE along with 95% confidence intervals.

A table of all anticipated and unanticipated deaths due to any cause, with number and frequency of such events in each arm/group of the clinical study, as well as the number of occurrences for each event. This also requires notification if the death is causally related to treatment for each reporting group.

A breakdown of the number and percentage of participants reporting each adverse event, categorized by System Organ Class (SOC) and preferred term (PT), will be presented. Note that counting will be by participant not event and participants are only counted once within each SOC and PT.

A further tabulation of these data, categorized by relationship to INOpulse, will be presented. Participants with multiple events within a particular body system or preferred term will be counted under the category of their drug-related event (related and not related) within SOC and PT. Relationship to INOpulse is categorized as related (rated "possible" or "related" in the CRF) or not related (rated "unlikely" or "not related" in the CRF).

A summary of events reported, categorized by severity, will also be provided. Participants with multiple events within a particular SOC and PT will be counted under the category of their most severe event in the following order: severe > moderate > mild within that SOC and PT.

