Table 14.3.2.6	Treatment-Emergent Adverse Events by System Organ Class, Preferred Term, and Relationship to IP	Full Safety Set
Table 14.3.2.7	Treatment-Emergent Adverse Events by System Organ Class, Preferred Term, and Maximum Severity	Full Safety Set
Table 14.3.2.8	Subjects with Adverse Events with Outcome of Death	Full Safety Set
Table 14.3.2.9	Subjects Who Experienced Serious Adverse Events	Full Safety Set
Table 14.3.3.1.1	Hematology Results by Time Point	Full Safety Set
Table 14.3.3.1.2	Biochemistry Results by Time Point – Chemistry	Full Safety Set
Table 14.3.3.1.3	Biochemistry Results by Time Point – Liver Function Tests	Full Safety Set
Table 14.3.3.1.4	Biochemistry Results by Time Point – Lipid/Protein Panel	Full Safety Set
Table 14.3.3.1.5	Biochemistry Results by Time Point – Factors/Other Proteins	Full Safety Set

Table Number	Title	Population
Table 14.3.4.1	Vital Sign Results by Time Point	Full Safety Set
Table 14.3.5.1	Electrocardiogram Results	Full Safety Set
Table 14.3.6	Physical Examination by Time Point	Full Safety Set
Figure 14.2.1.1	Forest Plot of Frequent Adverse Events	Full Safety Set
Listing 16.1.7	Randomization Assignments	All Randomized Analysis Set
Listing 16.2.1.1	Discontinued Subjects	All Randomized Analysis Set
Listing 16.2.1.2	Discontinuation of Investigational Product (IP)	All Randomized Analysis Set
Listing 16.2.2	Protocol Deviations	All Randomized Analysis Set
Listing 16.2.3.1	Subject Analysis Sets	All Screened Subjects
Listing 16.2.4.1	Demographic and Baseline Data	All Randomized Analysis Set
Listing 16.2.4.2	General Medical History	All Randomized Analysis Set
Listing 16.2.4.3	Prior and Concomitant Medications	All Randomized Analysis Set
Listing 16.2.5.1	Administration of Investigational Product – INO Pulse Usage	All Randomized Analysis Set
Listing 16.2.5.3	Treatment Compliance	All Randomized Analysis Set
Listing 16.2.6.1	NIAID Score Results	All Randomized Analysis Set
Listing 16.2.7.1	Treatment-Emergent Adverse Events	All Randomized Analysis Set
Listing 16.2.7.2	Non treatment-Emergent Adverse Events	All Randomized Analysis Set
Listing 16.2.7.3	Death Details	All Randomized Analysis Set
Listing 16.2.8.1	Hematology Results and Change from Baseline	Full Safety Set
Listing 16.2.8.2	Biochemistry Results and Change from Baseline	Full Safety Set
Listing 16.2.8.5	Pregnancy Test Results (Females of Childbearing Potential only)	Full Safety Set
Listing 16.2.9	Vital Signs	Full Safety Set
Listing 16.2.10	CT Scan Results	Full Safety Set

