Listing 16.2.11	X-Ray Results	Full Safety Set
Listing 16.2.12	Methemoglobin Results	Full Safety Set
Listing 16.2.13	Electrocardiogram Results	Full Safety Set
Listing 16.2.14	Physical Examinations	Full Safety Set

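### Methemoglobin values are only listed by subject, SpO2 values have no planned by-arm summary, and no by-arm AESI table fills the gap

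*SAP*

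**What the plan says.** Protocol 10.1.16 sets out what safety rests on: "Safety will be assessed throughout the study by monitoring vital signs, methemoglobin, SpO₂ and adverse events". Protocol 10.1.12 (and the synopsis) then gives the interruption rule: "If methemoglobin exceeds 7%, SpO₂ falls below 80%, or clinically significant iNO-related adverse events are observed, INOpulse therapy should be interrupted". An interrupted subject may restart at the investigator's discretion.

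The SAP handles these measurements as follows.

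- **Methemoglobin values (13.6.6):** "By-subject listings for physical examination, methemoglobin and 12-lead ECG findings will be provided". In Appendix 4 the only entry is Listing 16.2.12, "Methemoglobin Results".
- **Vital signs (13.6.5):** "Values for heart rate (HR), respiratory rate (RR), blood pressure (BP, systolic and diastolic), and temperature, and oxygen flow rate will be summarized", by arm and time point. SpO2 is not in that list.
- **AESIs (13.6.2):** the list includes methemoglobin at or above 7.0%, and any fall in PaO2 or SpO2 that the investigator considers clinically significant. Neither 13.6.2 nor Appendix 4 specifies an AESI table.
- **Discontinuations (13.6.2):** "An AE leading to treatment discontinuation is defined as an AE where action taken on study drug is Drug Withdrawn".

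**The concern.** Evaluating safety is the trial's secondary objective. Methemoglobin is the toxicity measure that the protocol monitors most closely for this gas, and SpO2 is the other measured quantity that can stop dosing. A reader would expect both to be compared between INOpulse and placebo. If the SAP is followed exactly, the report holds methemoglobin as pages of individual values, has no named output for SpO2, and has no by-arm count of subjects who crossed the limits the protocol sets. A systematic rise on active treatment that stays below the AESI threshold would not show in any planned table. If someone later decides to summarise these data, the choice of metric (mean, maximum, proportion above a cut-off) would be made after unblinding.

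**Working it through.** The documents give no figure to reproduce. The check sets the protocol's safety measures beside the SAP's outputs.

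| Protocol safety measure (10.1.16) | Interruption trigger (10.1.12) | By-arm summary of values in the SAP | Listing |
|---|---|---|---|
| Vital signs | No | Yes: 13.6.5, Table 14.3.4.1 | 16.2.9 |
| Methemoglobin | Yes, above 7% | None | 16.2.12 |
| SpO2 | Yes, below 80% | None | None titled for it |
| Adverse events | Yes, if clinically significant and related | Yes: 13.6.2, Tables 14.3.2.1 to 14.3.2.7 | 16.2.7.1, 16.2.7.2 |

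Two of the four measures have no by-arm summary of values. They are also the only two with numeric interruption limits.

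**Could another SAP section cover methemoglobin?** SAP 13.6.4 summarises laboratory parameters by arm. It names 7 chemistry items, 3 liver tests, 8 in the lipid/protein panel and 10 factors or other proteins: 7 + 3 + 8 + 10 = 28, plus CBC. Methemoglobin is not among them. Of the three items that share the sentence in 13.6.6, the other two each have a table in Appendix 4 as well as a listing: Table 14.3.5.1, "Electrocardiogram Results", and Table 14.3.6, "Physical Examination by Time Point". Methemoglobin alone has none, which suggests an oversight.

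**Does the AESI route fill the gap?** Only in part.

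1. The AESIs are defined, but no AESI summary is specified.
2. The methemoglobin criterion starts at 7.0%, so a shift below that level meets no criterion. Yet the protocol itself uses 3%, both as an exclusion limit (8.3) and as a condition for continuing after the start of treatment (10.1.12).
3. The SpO2 criterion depends on investigator judgement, not on the protocol's 80% limit.
4. The by-arm adverse event tables contain only what is recorded as an adverse event. I find no protocol rule that a methemoglobin or SpO2 value crossing a limit must be recorded as one. For laboratory results, Protocol 13.4.1 sends only those that qualify as adverse events to that form.

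**Interruptions.** The discontinuation definition counts only withdrawn drug. A subject interrupted on a methemoglobin or SpO2 limit and then restarted does not enter Table 14.3.2.4 for that event, and Appendix 4 has no interruption table.

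**How much data is involved?** Protocol 10.1.12 calls for half-hourly methemoglobin readings in the first hour (2), one at about 4 to 5 hours (1), then two a day. The expanded-access series (Protocol section 5) had a median treatment time of 4 days. With twice-daily readings on the 3 later days only, 2 + 1 + 2 × 3 = 9 post-dose readings. If they also apply on the first day, 2 + 1 + 2 × 4 = 11. That is roughly 9 to 11 per subject, assuming a similar treatment time in this trial.

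**The case against.** The best defence is that the safety picture is not empty. SAP section 13.0 makes summaries by treatment group the default. Events recorded as adverse events are tabulated by arm by system organ class, relationship and severity on the Full Safety Set. An unblinded DMC reviews AESIs (SAP 8.0). The protocol's single named safety endpoint, adverse events leading to discontinuation of study drug, is analysed. All of that stands, and it rules out several stronger readings that a reader might infer:

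- *That SpO2 is absent from the SAP.* It is in the AESI list and the glossary. Since Protocol 10.1.7 treats SpO2 under vital signs, its values may also appear in Listing 16.2.9, though the SAP does not say so.
- *That comparison with placebo is impossible.* Methemoglobin values and randomisation assignments are both listed. The comparison is unplanned, not impossible.
- *That a dose-related effect is hidden.* There is one active dose against placebo, so there is no dose-response to lose.
- *That nothing about interruptions is reported by arm.* Adverse events that trigger an interruption enter Tables 14.3.2.2 and 14.3.2.6 whether or not drug was withdrawn, and an exposure summary is planned (Table 14.3.1.1).
- *That the two 7% boundaries are an error.* One is a reporting definition and the other an interruption rule. They differ, and that calls only for reconciliation.

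A second objection is materiality. The expanded-access report found no methemoglobin increase above 1.5% in its first 25 patients, so crossings of 7% may be rare. That is fair, but if crossings are rare, the informative comparison lies below 7%, which is the part with no planned summary. The series is also small and uncontrolled. If all 25 contributed readings, 0 of 25 leaves a one-sided 95% upper bound of 1 − 0.05^(1/25) = 11.3% for the proportion exceeding 1.5%.

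A third objection is that SpO2 is hard to interpret when supplemental oxygen can be adjusted. That is correct, and it is a reason to read SpO2 beside the oxygen flow rate that 13.6.5 already summarises, not a reason to omit it.

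**Conclusion.** The point holds as a gap in planned safety reporting. Measured methemoglobin is listed only, measured SpO2 has no planned by-arm summary, and no AESI table by arm is specified. Two of the four named safety measures are affected. Sub-threshold shifts, and limit crossings that are not reported as adverse events, have no planned comparison with placebo. DMC oversight does not change this, because it does not commit the final report to a by-arm result.

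The consequence is limited to the secondary safety objective. Type I error, power and the primary analysis are untouched, and the documents give no evidence that crossings will be frequent. The conclusion rests on reading SAP 13.6.2 to 13.6.6 and Appendix 4 as the full set of planned safety outputs. The CRF and the DMC charter were not available.

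**What to change.** Amend SAP 13.6.2, 13.6.5, 13.6.6 and Appendix 4 to add, by arm on the Full Safety Set:

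- **(a) Methemoglobin table:** values by time point (baseline, the first-hour readings, 4 to 5 hours, then daily), change from baseline, on-treatment maximum, and the number of subjects crossing the protocol's own stated limits.
- **(b) SpO2 in the vital-sign table:** on-treatment minimum and the number of subjects below the protocol's stated limit, read alongside oxygen flow rate.
- **(c) AESI table:** one row for each category defined in 13.6.2.

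Also tabulate subjects with any study-drug interruption by arm, next to Table 14.3.2.4. Break this down by trigger only if the CRF records the reason. The protocol requires a documented reason for discontinuation (9.1) but does not say that one is recorded for interruption.

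Reconcile the methemoglobin boundary between SAP 13.6.2 (at or above 7.0%) and the protocol (above 7%). Which is right is for the sponsor to decide.

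The cost is SAP wording and a few output tables. Items (a) and (b) use values the protocol already collects, and (c) uses events already recorded. No new assessment and no change to any clinical rule is needed.
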